6.1. General points and methodology

✓ Methodology — trial design

Prospective, multicenter, randomized, controlled, open-label study, with blind evaluation of the primary criterion and several secondary criteria (PROBE design).

Parallel group design (1:1):

- The arm receiving the device under investigation: PA1704
- The arm receiving the comparator medical device: BioRoot™ RCS.

✓ Measures to reduce or avoid bias.

Randomization and stratification:

Before the trial is set up, the CRO's biostatistician will computer-generate a block randomization list stratified by clinical indication (initial endodontic treatment (ET) versus re-treatment (ER)). The randomization system will be integrated directly into the electronic CRF.

Randomization will be carried out by the electronic CRF once the eligibility criteria have been checked, the clinical indication (ET or ER) has been determined and all this information has been recorded in the specific module by the investigator.

It should be noted that the proportion of ERs will be 30% of the overall sample, which is close to the rate reported in a French Health Insurance survey (Masson 2002). The rate of ER may vary between sites: some investigators, because of their specialty in endodontics, will include a majority of patients with an indication for re-treatment, whereas GP investigators will probably have more indications for first-line treatment.

Blind:

Investigators and patients will not be blind to the medical device allocated due to the different ways in which the 2 products are presented and used. On the other hand, two independent qualified assessors (previously calibrated under the supervision of the study coordinator) will conduct the blind, centralized review of the retro-alveolar X-rays taken at TO (reference radiograph obtained immediately post-operatively), 6 months, 12 months, 24 months, 3.5 years and 5 years (Refer to Section "Equipment to be used to evaluate clinical trial variables and arrangements for monitoring maintenance and calibration." section of this chapter); they will be blinded to centre, patient, indication (initial or repeat endodontic treatment), and treatment arm; the files will first be anonymized by the CRO.

✓ Outcome measures

Primary criterion (composite criterion):

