The primary criterion is the **2-year efficacy rate of endodontic treatment** based on radiological criteria assessed blind by independent reviewers (complete healing, reduction of lesions, failure) AND clinical criteria assessed by the investigator (tooth functionality and pain).

Secondary criteria:

Reminder of secondary objectives	Secondary outcome measure	Time of evaluation (assessor)
Evaluation of the 6-month efficacy rate determined on the basis of radiological and clinical criteria	Radiological criteria (complete healing, reduction of lesions, failure) AND clinical criteria (tooth functionality and pain)	6 months (radiological criteria assessed by blind reviewers; clinical criteria assessed by investigator)
Evaluation of the 12-month efficacy rate based on radiological and clinical criteria	Radiological criteria (complete healing, reduction of lesions, failure) AND clinical criteria (tooth functionality and pain)	12 months (radiological criteria assessed by blind reviewers ; clinical criteria assessed by investigator)
Assessment of the 3.5-year efficacy rate of the endodontic treatment determined on the basis of radiological and clinical criteria (PA1704 arm only)	Radiological criteria (complete healing, reduction of lesions, failure) AND clinical criteria (tooth functionality and pain)	3.5 years ± 6 months (radiological criteria assessed by reviewers blind to the centre; clinical criteria assessed by the investigator)
Evaluation of the 5-year efficacy rate on the basis of radiological and clinical criteria (PA1704 arm only)	Radiological criteria (complete healing, reduction of lesions, failure) AND clinical criteria (tooth functionality and pain)	5 years ± 6 months (radiological criteria assessed byreviewers blind to the centre; clinical criteria assessed by the investigator)
Radiological evaluation of the quality of the apical filling (in terms of the level of apical filling, density and resorption of the extruded material)	Level of obturation at the X-ray apex (complete obturation, under-filling or over-filling)	T0 immediate post-op (investigator)
	Density: radiopacity and presence of vacuity	T0, 6 months, 12 months, 24 months for the 2 arms, And 3.5 years, 5 years for the PA1704 arm. (investigator + blind reviewer)
	Resorption of extruded material in the periapical space in the event of over-filling	6 months, 12 months, 24 months for the 2 arms, And 3.5 years, 5 years for the PA1704 arm. (investigator + blind reviewer)

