Measurement time and people in charge of evaluation:

For each criterion, this information is given in the table above.

Generally speaking, the assessment of performance and safety criteria begins with the root canal obturation.

Method of evaluating the efficacy rate of initial or repeat endodontic treatment (at 6 months, 12 months and 24 months for the 2 arms; and 3.5 years and 5 years for the PA1704 arm):

Therapeutic efficacy is a composite criterion based on the radiological data assessed **in blind conditions** by reviewers AND on the clinical data assessed **in an open-label manner** by the investigator at the follow-up visits at 6 months, 12 months, 24 months, 3.5 years and 5 years (only the PA1704 arm for the last 2 visits). With regard to the blind evaluation of the radiological criteria by two independent reviewers, the following clarifications are provided:

- The reviewers shall examine the anonymized retro-alveolar images (JPEG files as described in the imaging procedure in section "Equipment to be used to evaluate clinical trial variables and arrangements for monitoring maintenance and calibration." of this chapter) and answer the following questions:
 - Apical lesion: 1) Presence, absence or appearance of a lesion compared with the TO reference image? 2) In the case of a pre-existing lesion at TO, what is the evolution of the size of the lesion (reduction, stabilization or increase)?
 - Root canal filling density: 1) Is the radiopacity sufficient? 2) Presence of at least one bubble in the filling material?
 - Resorption of extruded material where applicable: Is the extruded material still present in the apical space?
- Timetable: 5 centralized image review campaigns are planned, one before each statistical analysis:
 - o 1st review campaign: At the end of the 6-month follow-up of all enrolled patients, a blind review of the T0 reference image and the 6-month follow-up image,
 - o ^{2nd} campaign: after 12 months' clinical follow-up of all patients, blind review of the 12-month check-up image,
 - o 3rd campaign: After 24 months of clinical follow-up for all patients, a blind review of the 24-month check-up image,
 - 4th campaign: After approximately 3.5 years of clinical follow-up of the patients treated with the PA1704 MD, a centre-blind review of the 3.5-year follow-up image,

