- Where appropriate (in the event of the appearance of a lesion or an increase in the size of a pre-existing lesion), notification of ET failure by the investigator: schedule retreatment.
- Complete the end-of-trial form at the end of the eCRF.

Table 7: Outline of the trial procedure

Actions	Participant	Visit V0 Selection	Visit V1 Enrolment (T0)	V1 + 7d	Visit V2 (within 45 days)	Visit V3 (M6 ± 1 month)	Visit V4 (M12 ± 1 month)	Visit V5 (M24 ± 1 month)	Visit V6 (3.5 years ± 6 months)	Visit V7 (5 years ± 6 months)
			Endo. treatment	Call tel.	Care follow- up	Clinical follow- up	Clinical follow- up	Clinical follow- up	Clinical follow-up PA1704 arm	Clinical follow-up PA1704 arm
Verification of the eligibility criteria	Investigator	x								
Trial information + Informed consent form	Investigator	х								
Collection of signed written consent form	Investigator		х							
Enrolment data: demographics, relevant history and treatments, COAD, CPITN, diagnosis of tooth to be treated	Investigator		х							
Randomization (1:1) with stratification	Investigator		х							
Surgical procedure for endodontic treatment + temporary coronal reconstruction	Investigator		х							
Retrieval of patient record (pain and AE over 7 days)	Investigator		x							
Post-op pain and AE assessment	Patient + Inv.			×						
Standard permanent coronal reconstruction	Investigator				X ^(a)					
Retro-alveolar image to be uploaded to eCRF	Investigator	х	x (immediate post-op)			х	х	х	х	х
Clinical examination (according to current practice): functional status of teeth + percussion test	Investigator				х	х	х	х	х	х
Evaluation of treatment quality and efficacy (X-ray	Investigator		х			х	х	х	х	х
criteria : apical lesion, filling density, material resorption)	independent reviewers		х			х	х	х	х	х
Vigilance (AE, defects)	Investigator									
Evaluation of comfort, cement use	Investigator		Х							

Legend: x: one-off action; continuous action, (a) care carried out by the investigator or by the patient's usual dental surgeon if the investigator is an exclusive endodontist.

6.5.3. Description of the activities carried out by the Sponsor's representatives (excluding monitoring).

None.

6.5.4. Any known or foreseeable factor likely to compromise the results of the clinical investigation or the interpretation of the results.

None.

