In addition, the difference in the 2-year efficacy rate between the 2 materials are to be calculated; its unilateral confidence interval of 95% will be provided and the lower limit is will be compared against the non-inferiority limit.

The main performance analysis will be carried out on the PP population, in accordance with the recommendations for non-inferiority studies. This will be complemented by an analysis of the mITT population to check the stability of the results.

7.7.5. Analysis of secondary performance criteria:

Efficacy rate at 6 months based on radiological and clinical criteria: Description and comparison, between the PA1704 arm and the BioRoot™ RCS arm, of the 6-month efficacy rate by Pearson's Chi-2 test or Fisher's exact test.

Efficacy rate at 12 months based on radiological and clinical criteria: Description and comparison, between the PA1704 arm and the BioRoot™ RCS arm, of the 12-month efficacy rate by Pearson's Chi-2 test or Fisher's exact test.

Quality of apical obturation at T0 (complete obturation, under-filling or over-filling): Description and comparison, between the PA1704 arm and the BioRoot™ RCS arm, of the proportions of apical obturation quality by Pearson's Chi-2 test or Fisher's exact test.

Density of root canal filling at T0, 6 months, 12 months, 24 months: Description and comparison at each time point, between the PA1704 arm and the BioRoot™ RCS arm, of the proportions of canals with an

obturation density deemed sufficient and the proportions of canals free of voids, by Pearson's Chi-2 tests or Fisher's exact tests.

Progress of material resorption over 24 months, in the event of over-filling at T0 (6 months, 12 months and 24 months): Description and comparison, between the PA1704 arm and the BioRoot™ RCS arm, of the proportions of patients with resorbed materials among patients who were over-filled at T0 by Pearson's Chi-2 test or Fisher's exact test.

Pre-operative and post-operative pain experienced by the patient (VAS 0-100 mm) at T0 (end of surgery), 12h, 24h, 48h, 72h and 7 days: For each time point, description and comparison of the pain, between the PA1704 arm and the BioRoot™ RCS arm, by a Student, Welch or Wilcoxon test. A figure representing average pain as a function of assessment times per arm will be provided. The causes of the pain will be described.

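### T0 obturation level is compared between arms but read only by the unblinded operator, and the plan does not say whose reading defines the over-filled subset for resorption

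*Combined protocol and SAP*

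**What the plan says.** **Who reads what.** Table 3 in Section 6.1 divides the radiological quality of the filling into three rows. Obturation level (complete, under-filled or over-filled) is listed as "T0 immediate post-op (investigator". The rows for density, which includes T0, and for resorption of extruded material each name the investigator and a blind reviewer. Section 6.1 makes Table 3 the governing statement on who evaluates and when: "For each criterion, this information is given in the table above".

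**Blinding.** Section 6.1 states that "Investigators and patients will not be blind to the medical device allocated". In Table 7 (Section 6.5.2) the investigator is also the participant responsible for "Surgical procedure for endodontic treatment + temporary coronal reconstruction". The person scoring the level is therefore the operator who placed the filling. Under V1 in Section 6.5.2, that score is recorded for each canal.

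**What the blinded readers do.** The first image campaign includes "a blind review of the T0 reference image and the 6-month follow-up image". Apart from the apical lesion questions, the readers are asked "Root canal filling density: 1) Is the radiopacity sufficient? 2) Presence of at least one bubble in the filling material" and "Resorption of extruded material where applicable: Is the extruded material still present in the apical space". The synopsis (Section 2.1) and Table 7 list the same three topics: lesion, density and resorption. None of the lists mentions obturation level.

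**How the readings are used.** Section 7.7.5 compares obturation quality at T0 between arms by a Pearson Chi-2 or Fisher exact test. It compares resorption "among patients who were over-filled at T0" and names no assessor for that condition.

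**The concern.** Obturation level is a judgement made on an image. When the person making it placed the filling and knows which device was used, the readings can differ between arms for reasons unrelated to the device. Independent blinded reading is the trial's own remedy: it is used for the radiological part of the primary criterion and, alongside the investigator's reading, for density and resorption. Obturation level lacks it, although Section 3.1.2 treats the apical level of filling as decisive for prognosis and Section 4.4 names under- and over-filling as the possible risks of the filling stage.

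Two comparisons are at stake. The first is the between-arm test of obturation quality. The second is resorption. Its denominator is the over-filled patients, and if their membership comes from the operator's call, blinded reading of the later images does not repair the selection. An over-fill missed at T0 leaves the denominator. A false over-fill call followed by a clear image could be counted as resorbed.

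**Working it through.** **Step 1: set the provisions side by side.** The plan states no figure on this point to reproduce.

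| Criterion | Assessor in Table 3 | On the blinded readers' list? | Use in Section 7.7.5 |
|---|---|---|---|
| Obturation level at T0 | Investigator only | No | Compared between arms |
| Density at T0 and later | Investigator and blind reviewer | Yes | Compared between arms |
| Resorption at 6, 12 and 24 months | Investigator and blind reviewer | Yes, where applicable | Compared among patients over-filled at T0 |
| Over-filling at T0 as the entry condition for resorption | None stated; the level row names only the investigator | Not asked as such | Defines the denominator |

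The first row is explicit. The last is a gap: neither Section 6.1 nor Section 7.7.5 says who decides that a patient was over-filled or when the resorption question applies.

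**Step 2: size, on assumed values.** The documents give neither an over-filling rate nor reader accuracy, so every rate below is an assumption.

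- Assumed: the same true over-filling rate *t* in both arms; operators record 70% of true over-fills in one arm and 90% in the other; no false over-fill calls. Nothing in the documents says which arm would have the lower detection.
- From Section 7.2: 80 patients enrolled per group and a minimum of 66.
- Observed rate = *t* × detection. Spurious difference = *t* × (0.90 − 0.70) = 0.20 × *t*. Expected subset = number of patients × observed rate.

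| True rate *t* | Observed rates | Spurious difference | Over-filled subsets of 80 | Over-filled subsets of 66 |
|---|---|---|---|---|
| 10% | 7% v 9% | 2 points | 5.6 v 7.2 | 4.6 v 5.9 |
| 20% | 14% v 18% | 4 points | 11.2 v 14.4 | 9.2 v 11.9 |
| 30% | 21% v 27% | 6 points | 16.8 v 21.6 | 13.9 v 17.8 |

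If detection is equal in the two arms, the spurious difference is zero. A true difference would then be shrunk by the detection factor.

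**Step 3: compare with sampling error.** With 80 per arm and observed rates of 14% v 18%, the standard error of the difference is √[(0.14 × 0.86 + 0.18 × 0.82)/80] = √(0.268/80) = 0.058, or 5.8 points. The 4-point bias is 4/5.8 ≈ 0.7 of a standard error. The same calculation gives 2/4.3 ≈ 0.5 at *t* = 10% and 6/6.7 ≈ 0.9 at *t* = 30%. Under these assumptions the bias is material but smaller than one standard error. The resorption subsets are small on any of these assumptions.

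**Step 4: reach.** Table 4 builds the primary criterion from the apical lesion, symptoms and function. Obturation level does not enter it, so the sample size and the non-inferiority conclusion do not depend on this point.

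**The case against.** The strongest reply has five parts.

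- **No promise is broken.** Section 6.1 commits to blind evaluation of the primary criterion and several secondary criteria, not all of them. This stands: the point is a design weakness, not a contradiction.
- **The subset may not be unblinded.** A reader might infer that the plan makes the operator's call the entry condition for the resorption comparison. The documents do not support that as a stated rule. Section 7.7.5 names no assessor, the readers' question applies only where relevant, and readers holding the T0 image could judge extrusion blind. This also stands. What remains is that the source is unspecified and the only named T0 assessor of over-filling is unblinded.
- **Details are deferred.** Section 7.7 leaves detail to a Statistical Analysis Plan, which Section 7.7.9 places before the first interim analysis. That plan could settle the source of the subset. It cannot supply a blinded reading of level if the readers are never asked for one.
- **The image is kept.** It is uploaded to the eCRF, so the loss is recoverable. That makes the fix easier but leaves the stated assessor unchanged.
- **The operator sees more.** The readers work from JPEG files, while the operator also has the intra-operative X-ray check. This is a reason to keep the operator's reading as a second source, not to make it the only one.

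A reader might also take obturation level to be the endpoint most closely tied to the change of presentation. The documents do not rank endpoints that way. Sections 3.4 and 6.2 speak of performance and safety in general, and Table 3 links operator comfort to the ready-to-use form more explicitly.

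**Conclusion.** The concern holds within limits. Table 3 leaves a criterion that is tested between arms to the unblinded operator alone, although blinded readers already review the same image. For resorption, the plan does not identify whose T0 reading defines the over-filled patients. Bias there is possible, not established.

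The effect is confined to secondary criteria. Its size cannot be derived from the documents. The range of about 2 to 6 points rests on assumed true rates of 10% to 30%, equal in both arms, and on assumed detection of 70% v 90% with no false calls. With no difference in detection there would be no spurious difference. The case for acting is that the remedy is cheap, not that a large bias has been shown.

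**What to change.** 1. In Table 3, add the blind reviewer as an assessor of T0 obturation level. Add a matching item to the blinded reader form for the first campaign: complete, under-filled or over-filled, for each canal. If that campaign is over, re-read the stored T0 images blind.
2. In Section 7.7.5 and the Statistical Analysis Plan, use the blinded reading for the between-arm comparison of obturation quality and to define the patients over-filled at T0. Keep the investigator's reading for care and as a sensitivity analysis.
3. State how disagreement between the two readers is resolved, and how per-canal scores become a patient-level classification. One possible patient-level rule is that a patient counts as over-filled if any canal is. The between-arm comparison should also state whether its unit is the canal or the patient.

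The cost is a small amount of extra reading time for the same two readers on about 160 images (2 × 160 = 320 image readings, more judgements for multi-canal teeth), plus the two written rules. The blinded reading is made from JPEGs without the intra-operative view, which is a limitation to note. No visit, procedure, sample size or primary analysis changes.

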The efficacy of **initial or repeated endodontic treatment** is affected by a number of preoperative clinical and technical factors. Clinically, pulp diagnosis, state of the canal (calcified canal, presence of a perforation) or the presence of a pre-operative peri-radical lesion can have a negative impact on the result. From a technical point of view, several root canal preparation and obturation techniques exist and studies have not led to the conclusion that one technique is superior to another (HAS 2008). Nevertheless, the level to which the root canal is filled at the apex is a deciding factor in the prognosis; full obturation of the root canal up to the X-ray apex is expected; in the case of under-filling (i.e. the canal is not completely filled and the X-ray image shows that the apical limit of the filler is less than 2 mm in relation to the X-ray apex), the result is a medium-term resumption of infection and necrosis of the remaining nervous and vascular tissues, leading to inflammation and pain and the need to undertake repeated endodontic treatment.

Based on two systematic reviews of the literature, Ng et al found that the efficacy rate (i.e. complete or partial cure) was 85.2% (IC95%: 82.2–88.3%) after initial root canal treatment and 77.2% (IC95%: 61.1–88.1%) after repeated endodontic treatment (Ng 2007; Ng 2008). These meta-analyses are based on dozens of clinical studies conducted over the last few decades, the methodologies for which vary widely, particularly in terms of the root canal filling cements used and the length of patient clinical follow-up after treatment (6 months to 20 years follow-up interval depending on the study; few studies had a follow-up of more than 4 years).

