3.1.3. Root canal obturation cements

There are different types of root canal cements. These include zinc oxide-Eugenol-based cements, resin-based materials and calcium silicate-based cements. Cement sealants are used in conjunction with gutta-percha cones. On the one hand, they bind the material to the canal walls and, on the other, they fill the spaces inaccessible to the gutta-percha material despite it being compacted (lateral canals and other branches). Together they are very stable and provide a good seal.

Calcium silicate-based cements are of interest in endodontics due to their physical-chemical and biological properties: these materials are **biocompatible**, **have antimicrobial activity and can promote healing of periapical tissues** (Zhang 2009; Zhang 2010). In addition to their radiopaque and adhesive properties, these cements have a hydrophilic profile, creating a moist environment close to the dentine (Koch and Brave 2010). Secondly, thanks to their malleability, they have a lower viscosity and a better sealing quality than other products. These cements produce hydroxyapatite, which creates a favorable environment for interacting with the dentine.

Bioroot™ RCS is a tricalcium silicate-based cement, developed by Septodont (Saint-Maur des Fossés, It is available as two products (powder and liquid) to be mixed;

the cement does not shrink during the setting phase, making the canal seal very airtight (Simon and Flouriot 2016). This sealing cement is indicated for the permanent filling of root canals in the case of inflamed or necrotic pulp, and also after a retreatment procedure. It is used in combination with gutta-percha using the single cone technique or cold lateral condensation. In a recently published clinical study comparing BioRoot™ RCS to resin-based cement (AH Plus), Zavattini et al (2020) reported a one-year complete or partial cure rate of 90% (95% CI: 80–96%; n=53 teeth treated with BioRoot™ RCS). Another clinical study comparing BioRoot™ RCS with zinc oxide-Eugenol cement (Pulp Canal Sealer) showed, in 39 patients who received BioRoot™ RCS for initial treatment (n=13) or retreatment (n=26), an overall one-year efficacy of 76.9% (95% CI: 61.6–87.3%) based on strict radiological criteria (i.e. complete cure; Bardini 2019). Finally, data collected

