 - o 5th campaign: After approximately 5 years of clinical follow-up of the patients treated with the PA1704 MD, a centre-blind review of the 5-year follow-up image.

By combining the responses relating to the radiological and clinical criteria, 3 levels of treatment efficacy are obtained: Effective treatment, Ineffective treatment, Efficacy uncertain (see table below).

Treatment efficacy will be evaluated using 2 complementary approaches:

- Main analysis on soft criteria: the rates of effective or uncertain treatment are compared with the rates of ineffective treatment,
- Secondary analysis based on strict criteria: rates of effective treatment are compared with rates of uncertain or ineffective treatment.

ТО	Check-ups at 6, 12 and 24 months							
Radiological criteria	Radiological criteria (blind reviewer)	Clinical criteria (investigator)	Conclusion Treatment efficacy rate					
No lesions	No lesions (complete healing)	asymptomatic, functional tooth	Effective treatment					
No lesions	Appearance of lesion (failure)	asymptomatic, functional tooth	Ineffective treatment					
No lesions	Appearance of lesion (failure)	symptomatic, non- functional tooth	Ineffective treatment					
Presence of lesion	No lesions (complete healing)	asymptomatic, functional tooth	Effective treatment					
Presence of lesion	Reduction in lesion size (incomplete healing)	asymptomatic, functional tooth	Effective treatment					
Presence of lesion	Reduction in lesion size (incomplete healing)	symptomatic, non- functional tooth	Efficacy uncertain					
Presence of lesion	Stabilization of lesion size	symptomatic or non- functional tooth	Ineffective treatment					
Presence of lesion	Stabilization of lesion size	asymptomatic tooth, functional tooth	efficacy uncertain					
Presence of lesion	Increase in lesion size (failure)	symptomatic or non- functional tooth	Ineffective treatment					
Presence of lesion	Increase in lesion size (failure)	asymptomatic tooth, functional tooth	Ineffective treatment					

Table 4: Evaluation of the efficacy of endodontic treatment based on clinical and radiological criteria.

✓ Equipment to be used to evaluate clinical trial variables and arrangements for monitoring maintenance and calibration.

Apart from the radiology equipment connected to a computer, no specific equipment is needed to collect the outcome measures.

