7.7. Statistical methods

The statistical methods are based on the following elements and will be detailed in the Statistical Analysis Plan.

7.7.1. Sample description:

The description of the subjects enrolled who completed the trial and those enrolled who left prematurely will be presented using a table of absolute (N) and relative (%) frequency. Reasons for premature discharge and deviations from the protocol will be listed.

7.7.2. Descriptive analyses:

Clinical data collected at enrolment and at each visit will be described. Descriptive statistics will be presented according to the nature of the criterion analyzed:

- Quantitative variable: sample size, number of missing data sets, mean, standard deviation, median, minimum and maximum;
- Qualitative variable: absolute frequencies (N) and relative frequencies (%) per class in each group, number of missing data.

Graphs will be provided for each variable.

7.7.3. Comparative analyses:

A comparison of 2 independent means will be made using the Student's t-test; if the variances are unequal (verified by the Fisher's test), use the Welch's test instead of the Student's test. If the conditions for applying the Student test are not met (n < 30), the non-parametric Wilcoxon test is used.

2 independent percentages are compared using Pearson's Chi-2 test. If the conditions for application are not met (at least one theoretical number < 5), Fisher's exact test is used.

7.7.4. Analysis of primary performance criterion:

As a reminder, the primary performance criterion is the efficacy rate at 24 months of treatment based on clinical criteria assessed by the investigator (tooth functionality and pain level) AND radiological criteria assessed blind by independent reviewers (complete healing, reduction of lesions, failure). In the event of failure at 6 or 12 months, the patient will be considered to have failed at 24 months.

The primary criterion will be analyzed using 2 approaches, in accordance with the literature:

- **Primary analysis of soft criteria**: treatment rates with complete or incomplete cure are compared against failure rates;
- **Secondary analysis of strict criteria**: treatment rates with complete healing are compared against rates of failure or incomplete healing (complete healing can take up to 4 or 5 years).

The comparison of efficacy rates between the 2 groups will be carried out using the Dunnett and Gent χ^2 test (Dunnett CW and Gent M 1977; Elie C et al 2008).

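### Section 6.1 and section 7.7.4 define soft (primary) and strict success differently, neither takes precedence, and Table 4 gives no result for a healed tooth that is symptomatic or non-functional.

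*Combined protocol and SAP*

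**What the plan says.** Section 5.2 states the hypotheses in terms of the 2-year rate under 'soft' radiological and clinical criteria, without defining soft. Two definitions follow.

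- **Section 6.1** classifies each tooth by Table 4 as effective, uncertain or ineffective. Soft: "Main analysis on soft criteria: the rates of effective or uncertain treatment are compared with the rates of ineffective treatment". Strict: "rates of effective treatment are compared with rates of uncertain or ineffective treatment".
- **Section 7.7.4 and the synopsis (Statistical Methods)** work from healing categories. Soft: "treatment rates with complete or incomplete cure are compared against failure rates". Strict: "treatment rates with complete healing are compared against rates of failure or incomplete healing".

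The primary criterion in 6.1 lists three radiological outcomes, "complete healing, reduction of lesions, failure". Yet the reviewers' questions and Table 4 in the same section also provide for a lesion of stable size. Section 7.7.10 describes the primary criterion as the rate of effective treatment, which is the label of the strict set in 6.1.

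The background supplies the planning rates. Section 3.1.3 reports a "one-year complete or partial cure rate of 90" per cent for the comparator. Section 3.1.2 says of initial treatment that "the efficacy rate (i.e. complete or partial cure) was 85.2" per cent; the reviews behind that figure are also cited for the 13% tolerance. Section 3.1.3 describes another study's result as "based on strict radiological criteria (i.e. complete cure".

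**The concern.** With two rules and no order of precedence, the same 24-month data can give more than one primary result and more than one strict result.

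Timing adds to the problem. Table 4 is headed for 6, 12 and 24 months, and sections 7.7.5 and 7.7.7 plan comparisons of efficacy between arms at 6 and 12 months. Section 7.7.9 allows minor modifications of the analysis strategy after each data review. If the rule is not settled before the 6-month review, results by arm under each reading could be known before the 24-month rule is chosen.

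The investigator scores symptoms and function open-label. Assigning the missing Table 4 combinations afterwards would therefore turn on data recorded with knowledge of the arm.

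**Working it through.** **1. The plan's own figure.** Inputs from sections 7.2 and 7.3: 90% in both arms, margin 0.13, one-sided 5%, power 80%.

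n = (1.645 + 0.842)² × 2 × 0.90 × 0.10 / 0.13² = 65.9, so 66 per arm. 66 × 1.2 = 79.2, so 80 enrolled per arm. Both figures reproduce, so the arithmetic is sound and the fault lies in the endpoint definition.

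**2. The two rules side by side.**

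| Tooth at 24 months | Table 4 class | Soft, 6.1 | Soft, 7.7.4 | Strict, 6.1 | Strict, 7.7.4 |
|---|---|---|---|---|---|
| Reduced lesion, asymptomatic and functional | Effective | success | success | success | non-success |
| Stable lesion, asymptomatic and functional | Uncertain | success | not cure, not named failure | non-success | not named |
| No lesion, symptomatic or non-functional | none | undefined | complete cure if read on the X-ray alone | undefined | complete healing if read on the X-ray alone |

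The first row is a direct contradiction for the strict set. The second is unreconciled for the primary set: under 7.7.4 the tooth could be a success, a non-success or left out.

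**3. Coverage of Table 4.** There are 2 radiographic courses without a lesion at T0 and 4 with one. 6 courses × 4 clinical states (symptomatic yes/no, functional yes/no) = 24 combinations.

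- If 'symptomatic, non-functional' is read as *or*: 18 listed, 6 unlisted. All 6 are teeth with no lesion at follow-up (3 for each T0 state).
- If read as *and*: 14 listed, 10 unlisted. The 4 extra are 2 reduced-lesion and 2 new-lesion combinations; the new-lesion ones are evidently ineffective.

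**4. Effect on the primary conclusion (illustrative counts).** At 66 per arm one tooth is 1/66 = 1.5 points. The Wald lower limit is d − 1.645 × √[p₁(1−p₁)/n₁ + p₂(1−p₂)/n₂]. The Farrington-Manning statistic is z = (d + 0.13)/SE₀, with SE₀ from the rates fitted under a difference of −0.13 (critical value 1.645).

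*Example A.* BioRoot: 59 healed or reduced, none stable, out of 66. PA1704: 55 healed or reduced, 2 stable and asymptomatic, 9 ineffective.

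*Example B.* PA1704: 57 of 66, none stable. BioRoot: 59 plus 2 stable.

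| Case | PA1704 v BioRoot | d (points) | SE (points) | Lower limit (points) | z | p |
|---|---|---|---|---|---|---|
| A, stable = success (6.1) | 57/66 v 59/66 | −3.03 | 5.68 | −12.37 | 1.675 | 0.047 |
| A, stable = non-success | 55/66 v 59/66 | −6.06 | 5.95 | −15.85 | 1.138 | 0.128 |
| A, stable left out | 55/64 v 59/66 | −3.46 | 5.77 | −12.94 | 1.578 | 0.057 |
| B, stable = success (6.1) | 57/66 v 61/66 | −6.06 | 5.33 | −14.83 | 1.240 | 0.107 |
| B, stable = non-success | 57/66 v 59/66 | −3.03 | 5.68 | −12.37 | 1.675 | 0.047 |

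In A, non-inferiority is shown under 6.1 and not shown if stable teeth are non-successes. Leaving them out makes the verdict depend on the test. In B the direction reverses.

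The documents do not write out the Dunnett-Gent statistic. Taking it, as an assumption, to be a Pearson chi-square on expected counts with the difference fixed at the margin gives z = 2.043 (57 v 59), 1.301 (55 v 59) and 1.606 (57 v 61). The verdicts for these equal-sized comparisons are the same.

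**5. Size for the strict set.** The retrospective study of another sealer in section 3.1.3 gives 83.1% complete + 7.8% incomplete = 90.9%. 0.078 × 66 = 5.1, so about 5 teeth per arm change strict class with the rule, if they are asymptomatic and functional.

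**The case against.** The strongest reply is that the outright contradiction concerns the strict analysis, which is secondary. On this view 6.1 and Table 4 are the operational rule for the primary analysis, and 7.7.4 is shorthand for it. Section 7.7 defers detail to a Statistical Analysis Plan, which 7.7.9 says will be written before the first interim analysis. The empty cells could be filled by inference: a reduced lesion on a symptomatic, non-functional tooth is already uncertain, so a healed one should be at least that. Finally, the examples sit at the boundary by construction.

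Part of this stands. The soft rules are unreconciled rather than flatly opposed, since 7.7.4 never calls a stable lesion a failure. The planned timing of the analysis plan reduces the risk of a choice made after seeing results. The numerical examples show sensitivity, not likelihood, and none of them uses the empty cells.

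The shorthand reading fails, however, because the strict sets in the two sections cannot be mapped onto each other. An analysis plan can add missing detail, but here it would have to choose between rules already in the protocol, and that choice fixes the primary success set. Inference about empty cells is no substitute for stating the result.

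**Conclusion.** The concern holds. The strict definitions contradict each other. The primary definition leaves the stable, asymptomatic lesion a success in one place and unassigned in another. Table 4 lacks a result for 6 of 24 combinations on any reading. No text says which rule prevails.

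Near the margin, an imbalance of two stable teeth at 66 per arm is enough to change the conclusion, in favour of either arm. How likely that is cannot be stated without a stable-lesion rate.

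The planning rate matches 7.7.4 in wording (complete or partial cure), but the documents do not say how its sources classed stable or symptomatic teeth. The separate analysis plan announced in 7.7 is not among the documents and might address the point. This must be fixed, because the primary success set is not uniquely defined.

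**What to change.** Before the first (6-month) outcome review:

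- State one soft and one strict definition and use them in the synopsis, 6.1, 7.7.4 and 7.7.10.
- Say where a stable, asymptomatic lesion falls in the primary analysis.
- Give every Table 4 combination a result, including healed teeth that are symptomatic or non-functional, and say whether the comma means *and* or *or*.
- Pre-specify the other soft rule (with or without uncertain as success) as a sensitivity analysis.

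Two consistent options, with the choice left to the sponsor:

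- **(a)** Soft = complete or incomplete healing on an asymptomatic, functional tooth (Table 4 effective, in line with 3.1.2); strict = complete healing only. This takes all uncertain teeth out of soft success, including reduced lesions on symptomatic, non-functional teeth.
- **(b)** Keep effective or uncertain as soft success, align 7.7.4 and the synopsis to it, and say whether the 90% planning rate still applies.

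The cost is wording, table rows and one extra analysis of data already collected, with a protocol amendment under section 9 if the primary success set changes. If the expected rate under the chosen rule is below 90%, the power should be restated. At 66 per arm with equal true rates, exact power by Farrington-Manning is 77% at 90%, 70% at an assumed 87% and 66% at an assumed 85%; with a Wald limit it is 80%, 72% and 68%.
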